12.2 Populations for Analysis

12.2.1 Definition of Analysis Populations

The Safety population will include all randomized subjects who complete at least one use of study product. This population will be based on the study product the subject received. All assessments of safety will be based on this analysis population.

The modified Intent-To-Treat (mITT) population will include all randomized subjects who complete at least one use of study product and have at least one post treatment efficacy assessment. This population will be based on the study product to which the subject was randomized. All assessments of efficacy will be primarily based on this analysis population.

The per protocol (PP) population is defined as all subjects in the mITT population who have at least one assessment of efficacy considered unaffected by protocol violations.

12.2.2 Exclusions of Data from Analysis

Exclusion of any data from the analyses will be determined during a Blinded Data Review (BDR) Meeting prior to database lock. Any reasons for exclusion from an analysis population will be listed, if applicable.

A PP analysis will be performed on the primary endpoint if there is more than 10% difference in the number of subjects between the PP and mITT populations. A decision on whether a PP analysis will be performed will be made prior to study unblinding (release of the randomization codes).

12.3 Statistical Analyses

This section is a summary of the planned statistical analyses focusing on the primary and secondary endpoints in detail with a brief overview for other endpoints. Additional details of all the proposed statistical analysis will be documented in the statistical analysis plan (SAP), which will be written following finalization of the protocol and prior to study unblinding.

12.3.1 Primary Analysis

The mean breath organoleptic score at a visit / time point will be derived across all of the recorded organoleptic scores recorded at the visit / time point.

The primary endpoint for the study is the change in mean breath organoleptic score from Baseline (pre-brushing) to 3 weeks (pre-brushing) and the comparison between the Experimental and Reference Dentifrices in the mITT population. This will be assessed at the two-sided 5% significance level.

An ANCOVA model will be used to analyze the change in mean breath organoleptic score from Baseline (pre-brushing) to 3 weeks (pre-brushing) with study product and gender as fixed effects and the mean Baseline (pre-brushing) breath organoleptic score as a covariate. The least square means for each study product will be presented based on observed margins and used to test for < 0 change from baseline. The difference between least square means for the

Experimental Dentifrice compared to the Reference Dentifrice will be presented and used to test for a difference between products. The two-sided p-values and 95% confidence intervals will be provided.

The assumption of normality and homogeneity of variance in the ANCOVA will be investigated. In case of violation of these assumptions, a suitable nonparametric test (adjusted for gender) will be performed, and results will be provided to support the ANCOVA results.

The mean pre-brushing breath organoleptic score values across the study and change from baseline will be summarised descriptively.

12.3.2 Secondary Analyses

All secondary endpoint analyses will be performed on the mITT population. There will be no adjustment for multiplicity in the analyses described in this section.

Volatile Sulfur Compounds (VSC)

There will be individual evaluations of hydrogen sulfide, methanethiol and dimethyl sulfide concentrations in breath taken at each visit (Baseline and Week 3) at each time point (pre-brushing /1-hour post- brushing). The Total VSC at a visit/time point will have two samples. This will be derived as the sum of the hydrogen sulfide, methanethiol and dimethyl sulfide concentrations in breath and then the mean over two samples to derive one value used for analysis per visit/timepoint. The sum and the average will be performed on the raw scale and final value will be transformed.

For each concentration (hydrogen sulfide, methanethiol, dimethyl sulfide, Total VSC), the result will be log (base 10) transformed. Details of handling zero values will be detailed in the SAP.

The ANCOVA models described below will be applied for each of the mean concentrations using a different definition of Baseline and post-baseline as follows:

- Baseline = Baseline (pre-brushing), Post-baseline = Week 3 (pre-brushing)
- Baseline = Baseline (pre-brushing), Post-baseline = Week 3 (1-hour post-brushing)
- Baseline = Baseline (pre-brushing), Post-baseline = Baseline (1-hour post-brushing)
- Baseline = Week 3 (pre-brushing), Post-baseline = Week 3 (1-hour post-brushing)

The appropriate change from Baseline in the logged value will be analyzed for each post-baseline concentration using an ANCOVA model with study product and gender as fixed effects and the respective logged mean Baseline concentration as a covariate. The least square means for each study product will be based on observed margins to test for < 0 change (on the logged scale) from baseline. The difference between least square means for the Experimental Dentifrice compared to the Reference Dentifrice will be used to test for a difference between products. As well as presenting the least square means and differences on the log scale, the corresponding back transformed values (antilog base 10) will be presented to represent percent reduction from baseline and percent difference from control relative to baseline. The two-sided p-values and 95% confidence intervals (logged and back-transformed) will be provided.

The raw and logged concentration (hydrogen sulfide, methanethiol, dimethyl sulfide, Total VSC) values across the study and changes from baseline (for each type of baseline detailed above) will also be summarised descriptively.

Organoleptic score

The primary analyses described in [Section 12.3.1](#) will be repeated but will instead use the following as the Baseline and post-baseline mean breath organoleptic score definitions:

- Baseline = Baseline (pre-brushing), Post-baseline = Week 3 (1-hour post-brushing)
- Baseline = Baseline (pre-brushing), Post-baseline = Baseline (1-hour post-brushing)
- Baseline = Week 3 (pre-brushing), Post-baseline = Week 3 (1-hour post-brushing)

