12 STATISTICAL CONSIDERATIONS AND DATA ANALYSES

12.1 Sample Size Determination

Sufficient subjects will be enrolled to randomize approximately 106 subjects to have at least 100 complete the study (at least 50 subjects per treatment arm). It is considered sufficient to have 100 subjects complete in this study to meet the study's objectives. The subjects will be stratified by their sex prior to randomization.

Existing GSKCH studies were referred to for information and data to enable calculation of an appropriate power and sample size however no relevant information was observed for a 3-week study in a gingivitis population as planned for this study.

Data from a published study that evaluated halitosis in subjects with gingivitis and periodontitis ([Pham et al., 2011](#)) was taken into consideration to provide information regarding the variability and sample size for this endpoint. The sample size in this literature was N=116 for the gingivitis population and the variability estimate was observed to be 0.46 for the organoleptic score. The scoring was on a 5-point scale with very similar descriptors to those to be used in this study however only one assessor was used for organoleptic score assessment (as opposed to 3

assessors which will be used in this study). Considering the number of assessors in this study, the standard deviation was estimated to be 0.265 (0.46/sqrt(3)).

Using the standard deviation of 0.265, for 50 subjects per arm (100 subjects completing the study) the detectable mean difference is estimated to be 0.15 for 80% power and alpha=0.05.

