3.1 Baseline Definition

For all endpoints, the baseline value will be the Day 0 (Visit 2) pre-brushing assessment with a non-missing value.

For secondary endpoints VSC and Organoleptic score, analysis is based on two baselines. One is as mentioned above Day 0 (Pre-brushing) and other is Week 3 (Pre-brushing).

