4.4.2 Secondary Efficacy Variables

All secondary endpoint analyses will be performed on the mITT population. There will be no adjustment for multiplicity in the analyses described in this section.

Secondary efficacy endpoints are:

- Mean total VSC concentration in breath.
- Mean hydrogen sulfide, methanethiol and dimethyl sulfide concentration in breath.
- Mean breath organoleptic scores.

Secondary efficacy variables are defined as:

- Change from baseline (pre-brushing) to 3 weeks (pre-brushing) in mean total VSC concentration in breath.

- Change from baseline (pre-brushing) to 3 weeks (pre-brushing) in mean hydrogen sulfide, methanethiol and dimethyl sulfide concentration in breath.
- Change from baseline (pre-brushing) to 3 weeks (1 hour post-brushing) in mean total VSC concentration in breath.
- Change from baseline (pre-brushing) to 3 weeks (1 hour post-brushing) in mean hydrogen sulfide, methanethiol and dimethyl sulfide concentration in breath.
- Change from baseline (pre-brushing) to 3 weeks (1 hour post-brushing) in mean breath organoleptic scores.
- Change from pre-brushing to 1 hour post brushing at Baseline and after 3 weeks in mean total VSC concentration in breath.
- Change from pre-brushing to 1 hour post brushing at Baseline and after 3 weeks in mean hydrogen sulfide, methanethiol and dimethyl sulfide concentration in breath.
- Change from pre-brushing to 1 hour post brushing at Baseline and after 3 weeks in mean breath organoleptic scores.

4.4.2.1 Secondary Efficacy Variable 1

Mouth air VSC determination will be performed pre- and 1 hour (± 5 minutes) post-brushing at Visits 2&3. The mouth air sample will be evaluated using the OralChroma Halitosis Measuring instrument (Model CHM-2 [Nissha FIS, Inc.; Osaka, Japan]) in agreement with the manufacturer's instructions. The OralChroma is a portable gas chromatograph with a highly sensitive semiconductor gas detector which can determine the concentration of the 3 main VSCs in breath (hydrogen sulfide, methane thiol and dimethyl sulfide).

There will be individual evaluations of hydrogen sulfide, methanethiol and dimethyl sulfide concentrations in breath taken at each visit (Baseline and Week 3) at each time point (pre-brushing /1-hour post-brushing).

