4.4.2.1.1 Statistical Hypothesis, Model and Method of Analysis

Study product differences will be tested under the null hypothesis:

- H_0 : There is no treatment difference
- H_1 : There is a treatment difference

The following study product comparisons will be analyzed:

- Experimental Dentifrice versus Reference Dentifrice

The ANCOVA models described below will be applied for each of the mean concentrations using a different definition of Baseline and post-baseline as follows:

- Baseline = Baseline (pre-brushing), Post-baseline = Week 3 (pre-brushing)
- Baseline = Baseline (pre-brushing), Post-baseline = Week 3 (1-hour post-brushing)
- Baseline = Baseline (pre-brushing), Post-baseline = Baseline (1-hour post-brushing)
- Baseline = Week 3 (pre-brushing), Post-baseline = Week 3 (1-hour post-brushing)

All concentration values will be log (base 10) transformed including baseline for each parameter. The corresponding change from baseline in the logged value will be analyzed for each postbaseline concentration (hydrogen sulfide, methanethiol, dimethyl sulfide, Total VSC) using an ANCOVA model with study product and gender as fixed effects and the respective logged mean Baseline concentration as a covariate. The least square means for each study product will be based on observed margins to test for < 0 change (on the logged scale) from baseline. The difference between least square means for the Experimental Dentifrice compared to the Reference Dentifrice will be used to test for a difference between products. As well as presenting the least square means and differences on the log scale, the corresponding back transformed values (antilog base 10) will be presented to represent percent reduction from baseline and percent difference from control relative to baseline. The two-sided p-values and 95% CIs (logged and back-transformed) will be provided.

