Using the above model for each of the definition mentioned above, adjusted mean change [log (base 10)-based] from each baseline and percent reduction (back-transformed) from each baseline, along with corresponding 95% CIs will be reported by study product group will be provided for each concentration parameters (hydrogen sulfide, methanethiol, dimethyl sulfide, Total VSC) respectively in Table 14.2.3.2.1, Table 14.2.3.2.2, Table 14.2.3.2.3, Table 14.2.3.2.4 (with baseline as Day 0 pre-brushing) and respectively in Table 14.2.3.3.1, Table 14.2.3.3.2, Table 14.2.3.3.3, Table 14.2.3.3.4 (with baseline as Week 3 pre-brushing). Also, p-

values testing for negative change from baseline will be presented for study product groups. Mean difference between study product groups [Log (base 10) based], percent difference (back-transformed) from control relative to each baseline, corresponding 95% CIs and p-values will be provided for each concentration parameters (hydrogen sulfide, methanethiol, dimethyl sulfide, Total VSC) respectively in Table 14.2.3.2.1, Table 14.2.3.2.2, Table 14.2.3.2.3, Table 14.2.3.2.4 (with baseline as Day 0 pre-brushing) and respectively in Table 14.2.3.3.1, Table 14.2.3.3.2, Table 14.2.3.3.3, Table 14.2.3.3.4 (with baseline as Week 3 pre-brushing). This will be assessed at the two-sided 5% significance level.

The assumption of normality and homogeneity of variance in the above described ANCOVA analyses will not be investigated, because the analysis will be performed on log (base 10) transformed data.

4.4.2.2 Secondary Efficacy Variable 2

Secondary endpoint is the change in mean breath organoleptic score:

At following Baseline and post-baseline definitions:

- Baseline = Baseline (pre-brushing), Post-baseline = Week 3 (1-hour post-brushing)
- Baseline = Baseline (pre-brushing), Post-baseline = Baseline (1-hour post-brushing)
- Baseline = Week 3 (pre-brushing), Post-baseline = Week 3 (1-hour post-brushing)

Descriptive statistics (n, mean, SD, SE, median, minimum, and maximum) will be presented for mean breath organoleptic score at each assessment time point in Table 14.2.2.1.1 for all subjects in mITT population by study product. Raw means (\pm SE) of the mean breath organoleptic score at each time point will be plotted by study product in Figure 14.2.1.1 for all subjects in mITT population.

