4.4.2.2.1 Statistical Hypothesis, Model and Method of Analysis

Study product differences will be tested under the null hypothesis:

- H_0 : There is no treatment difference
- H_1 : There is a treatment difference

The following study product comparisons will be analyzed:

- Experimental Dentifrice versus Reference Dentifrice

A similar ANCOVA model as used for the primary analysis (as described in [Section 4.4.1.2](#)) will be used but with the appropriate pre-brushing and post-baseline result used accordingly.

Using the above model for each of the definition mentioned above, adjusted mean change from each baseline, along with 95% CIs will be reported by study product group will be provided for mean breath organoleptic score in Table 14.2.4.1 (with baseline as Day 0 pre-brushing) and

Table 14.2.4.2 (with baseline as Week 3 pre-brushing). Also, p-values testing for negative change from baseline will be presented for study product groups. Mean difference between study product groups, 95% CIs and p-values will be provided for mean breath organoleptic score in Table 14.2.4.1 (with baseline as Day 0 pre-brushing) and Table 14.2.4.2 (with baseline as Week 3 pre-brushing). This will be assessed at the two-sided 5% significance level.

The assumption of normality and homogeneity of variance in the ANCOVA will be investigated. In case of violation of these assumptions, a suitable nonparametric test (the Van Elteren test, adjusted for gender) will be performed, and results will be provided to support the ANCOVA results. If the inferences from the two analyses are similar, then both sets of results will be reported and emphasis will be made on the ANCOVA results. In case of discrepancies between inferences of the ANCOVA and non-parametric analysis, results will be drawn from the non-parametric analysis.

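### Five Week 3 one-hour models adjust for the Week 3 pre-brushing value, which is measured after randomisation, so their product test is not a test of the stated difference in one-hour change

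*Protocol*

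**What the plan says.** Randomisation takes place at Visit 2, after the Day 0 pre-brushing assessment (protocol Section 8.2.1). One secondary objective compares products on the change within a visit. For the organoleptic score, SAP Section 4.4.2 words this as "Change from pre-brushing to 1 hour post brushing at Baseline and after 3 weeks in mean breath organoleptic scores", and it has matching entries for total VSC and the three gases.

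For the Week 3 part of that objective, protocol Section 12.3.2 sets "Baseline = Week 3 (pre-brushing), Post-baseline = Week 3 (1-hour post-brushing", once for the VSC variables and again for the organoleptic score. SAP Section 3.1 confirms two baselines for these endpoints: "One is as mentioned above Day 0 (Pre-brushing) and other is Week 3 (Pre-brushing".

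The covariate follows the baseline:

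- **VSC (SAP 4.4.2.1.1):** the ANCOVA has product, gender "and the respective logged mean Baseline concentration as a covariate".
- **Organoleptic score (SAP 4.4.2.2.1):** a model like the primary one "will be used but with the appropriate pre-brushing and post-baseline result used accordingly".

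The results go to Tables 14.2.3.3.1 to 14.2.3.3.4 and 14.2.4.2, all marked as topline in SAP Appendix 1. Each product comparison is assessed at the two-sided 5% level, with no multiplicity adjustment for secondary endpoints.

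**The concern.** Week 3 pre-brushing is not a baseline in the randomisation sense. It is an outcome, and for the organoleptic score it is the very measurement on which the primary endpoint rests. An ANCOVA compares the arms at a common value of its covariate. If the product lowers the Week 3 pre-brushing value, the model compares experimental and reference subjects whom randomisation did not make alike, and it removes only part of the three-week effect from the one-hour contrast.

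The product p-value then mixes the three-week effect with the one-hour response. A product whose three-week benefit simply persists to one hour, with no additional one-hour effect, could be reported as having one. With a slope above 1 it could be reported as having a disadvantage. Neither document restates the comparison as conditional on the Week 3 level or says how this p-value is to be read.

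**Working it through.** **Inputs from the documents** (protocol Section 12.1): 50 completers per arm; two-sided alpha 0.05; SD 0.265, derived from a single-assessor source, where "the variability estimate was observed to be 0.46 for the organoleptic score"; detectable difference 0.15.

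**The plan's own figure.** 0.46/√3 = 0.266, given as 0.265. Detectable difference = (1.960 + 0.842) × 0.265 × √(2/50) = 0.148, which rounds to the stated 0.15.

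**Algebra.** Let X be the Week 3 pre-brushing value, Y the Week 3 one-hour value, dX and dY the arm differences (experimental minus reference), and b the pooled within-arm slope of Y on X.

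- Stated contrast, the difference in mean change: dY − dX.
- Product coefficient from ANCOVA of Y − X on product, gender and X: dY − b·dX.
- Gap: (dY − b·dX) − (dY − dX) = (1 − b)·dX.

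Least square means at observed margins do not remove the gap, because both arms are evaluated at one common X.

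**Size for the organoleptic score.** Assumed: dX = −0.15, carried through in full to one hour (dY = −0.15), so the true difference in one-hour change is 0. Scores are normal, with equal SD and common correlation b at Day 0, Week 3 pre-brushing and Week 3 one hour. 60,000 simulated trials per cell.

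| b | Gap (1 − b) × (−0.15) | Planned model rejects, SD 0.265 | Planned model rejects, SD 0.46 | Day 0 covariate, or product and gender only |
|---|---|---|---|---|
| 0.3 | −0.105 | 50% | 21% | 5% |
| 0.5 | −0.075 | 34% | 15% | 5% |
| 0.7 | −0.045 | 20% | 10% | 5% |
| 0.9 | −0.015 | 9% | 7% | 5% |

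**Boundary cases.**

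- No three-week effect (dX = 0): the planned model rejects in 5%.
- Slope 1.0: gap 0, rejection 5%.
- Slope 1.2 (post-brushing SD 1.5 times pre-brushing, correlation 0.8; 1.5 × 0.8 = 1.2): gap (1 − 1.2) × (−0.15) = +0.03. Rejection is 9% at SD 0.265 and 6% at SD 0.46, mostly in favour of the reference. A slope above 1 is conceivable for VSC if zeros, set to 0.01 before the log10 transform (SAP 4.4.3), are commoner after brushing.
- Masking: with dX = −0.15, b = 0.5 and a true difference in change of +0.075, the planned model averages 0.000 and rejects in 4.5%, against 28.6% for the plain change comparison (8,000 trials).

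**Size for VSC.** On the log10 scale, if the Week 3 pre-brushing level is a fraction r lower and this carries through, the apparent extra reduction is 1 − 10^((1 − b)·log10(1 − r)), that is 1 − (1 − r)^(1 − b).

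| b | r = 10% | r = 30% |
|---|---|---|
| 0.3 | 7% | 22% |
| 0.5 | 5% | 16% |
| 0.7 | 3% | 10% |
| 0.9 | 1% | 4% |
| 1.2 | 2% increase | 7% increase |

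**Does the non-parametric back-up help?** SAP 4.4.2.2.1 says that if ANCOVA assumptions fail, "a suitable nonparametric test (the Van Elteren test, adjusted for gender) will be performed", but it does not name the variable tested. In the full carry-through cases (5,000 trials each), Van Elteren on the unadjusted change rejects in 4.4 to 5.4%. On a change adjusted for Week 3 pre-brushing it rejects in 45/30/18/8% (SD 0.265) and 20/14/9/6% (SD 0.46) at b = 0.3/0.5/0.7/0.9. For VSC there is no such route: "The assumption of normality and homogeneity of variance in the above described ANCOVA analyses will not be investigated".

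**The case against.** The strongest reply is that this is a choice between change score and ANCOVA, not an error. Among subjects with the same Week 3 pre-brushing value and b below 1, experimental users do have lower one-hour values in the full carry-through case, and the planned model reports that correctly. That is true, but the documents do not state the conditional question, and randomisation does not protect it.

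A second reply is that the plain change contrast can mislead too. If brushing brings both arms to the same one-hour level, the change contrast is +0.15 against the experimental product, because that arm started lower. With the Day 0 covariate it is significant in 65/80/95/100% of trials at b = 0.3/0.5/0.7/0.9 with SD 0.265, and 27/36/54/95% with SD 0.46. The planned model rejects less often there, in 13/34/75/100% and 8/15/34/91%. This stands as a caution about reading the endpoint. It is not a fault of the test, since the difference in change really is +0.15. The planned Day 0-to-Week 3 one-hour comparison then shows 0.00 with 5% rejection, so the two have to be read together.

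Several smaller points also stand. The slope, the three-week effect and the carry-through pattern are assumptions, and the simulation ignores the discrete 0–5 scale. No error rate was computed for VSC. If Van Elteren is triggered and disagrees with ANCOVA, the SAP lets it prevail, which could repair the organoleptic model alone. Unadjusted VSC changes and organoleptic means by product are to be tabulated, so the raw contrast will be visible, but untested.

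**Conclusion.** The concern holds. The five models do not test the difference in one-hour change that the plan names, except when there is no three-week effect or the within-arm slope is exactly 1. The shift of (1 − b)·dX is a matter of algebra; its size depends on quantities the documents do not give. Over the assumed slopes of 0.3 to 0.9, with a three-week effect equal to the plan's detectable difference, rejection under no difference in one-hour change runs from 9 to 50% at SD 0.265 and 7 to 21% at SD 0.46. The problem arises when the product has worked at three weeks, which is the case of most interest.

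The reach is limited: one of four VSC contrasts and one of three secondary organoleptic contrasts. The primary analysis and every comparison with Day 0 pre-brushing as baseline are unaffected. The change should be made because it is cheap and the results are destined for topline reporting, but it does not threaten the main conclusion.

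**What to change.** Keep the within-visit Week 3 change as the endpoint in all five models and replace the Week 3 pre-brushing covariate with Day 0 pre-brushing. A model with product and gender only is equally valid; in the cells simulated here the Day 0 covariate made the standard error about 0.5% larger, so there is little to choose between them. In addition:

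- State that Van Elteren for this contrast, if triggered, uses the unadjusted within-visit change.
- Show any Week 3-adjusted version as descriptive, without a between-product p-value.
- State that the change contrast is read beside the planned Day 0-to-Week 3 one-hour comparison.

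The edits fall in the protocol synopsis (statistical analysis) and Section 12.3.2, SAP Sections 3.1, 4.4.2.1.1 and 4.4.2.2.1, Tables 14.2.3.3.1–4 and 14.2.4.2, and raw outputs 16.1.9.2.2.1–4 and 16.1.9.3.2. No new data are needed.

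The price is some precision. Relative to the planned model, the standard error with the Day 0 covariate at b = 0.3/0.5/0.7/0.9 changes by +19/+11/+4/−1% (SD 0.265) or +22/+14/+7/+1% (SD 0.46) when dX = −0.15, and by +24/+15/+8/+3% with no three-week effect.

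A lighter fallback is to keep the models, state that they compare products at equal Week 3 pre-brushing level, and label them exploratory. That makes the reporting honest but leaves the stated endpoint without a test.
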